## 6.6.2 Monitoring of Renal Function and Dose Adjustment

The dose of study intervention can be adjusted at the discretion of the investigator to account for renal function following the recommendations displayed in the table below [Table 6–3](#).

**Table 6–3 Renal Function Evaluation During Study**

eGFR (mL/min/1.73 m  ) at any time after randomization	Action to be taken
Decrease ≥25% and <40% from baseline	
 
Check for potential reversible causes:           
 
Concomitant medications known to affect renal function (e.g. NSAIDs, antibiotics)
 
Adverse event (e.g. urinary infection, urinary retention, dehydration)
 
 
 
Address potential reversible causes if considered clinically appropriate
 

Decrease ≥40% from baseline	
 
Check for potential reversible causes and address, as above.
 
At the investigator's discretion, study drug can be down-titrated or interrupted as follows:           
 
Further monitor eGFR/creatinine
 
If eGFR/creatinine has reached acceptable levels (to be determined for the individual participant), please re-start study intervention at the next lower dose level (or dose level 1 if the participant was already on this dose).
 
 
 
Re-test at central laboratory after 4 weeks to confirm eGFR decrease of ≥50% or ≥57%*
 

Abbreviations: eGFR = estimated glomerular filtration rate; NSAID = non-steroidal anti-inflammatory drug

\* Decrease based on central laboratory data.

## 6.7 Intervention After the End of the Study

No intervention is planned following the end of the study.

## 7. Discontinuation of Study Intervention and Participant Discontinuation/Withdrawal

### 7.1 Discontinuation of Study Intervention

After randomization, discontinuation of study intervention (for any reason) does not constitute the participants' withdrawal from the study (see also Section [7.2](#)).

Study intervention must be prematurely and permanently discontinued if any of the following occurs:

- Pregnancy of the participant (see also Section [8.3.5](#))
- The investigator is of the opinion that continuation of treatment with study intervention is harmful to the participant's well-being
- The randomization code is broken by the investigator, or other responsible person, when knowledge of the participant's treatment is required
- Any investigational drug other than the study intervention is used.
- Treatment with an MRA (eplerenone, spironolactone, canrenone, esaxerenone) for a period of more than 2 weeks.

Study intervention *may* be prematurely and permanently discontinued if any of the following occurs:

- Any suspected drug-related AE or SAE
- If any exclusion criterion applies during treatment
- If a significant violation of the protocol occurs, as defined by the sponsor and the coordinating investigator.

Participants who prematurely and permanently discontinue study intervention are expected to continue in the post-treatment follow-up period and to attend all protocol-specified study visits, and should be encouraged to perform all scheduled assessments described in the SoA for premature discontinuations ([Figure 1–2](#)).

Under certain circumstances, should the reason for permanent discontinuation of study intervention change, making it no longer applicable and the investigator is of the opinion it is in the subject's best interest to restart treatment, study intervention may be restarted on a case-by-case basis following comprehensive review by the Study Medical Expert.

If a participant no longer on study intervention is unable to attend the clinic for a study visit, a telephone consultation may be performed to determine if relevant health events /endpoints (e.g. development of CV or renal complications) have occurred. Ideally, a face-to-face visit should be performed at least once a year. The End of Study (EOS) visit is expected to be an onsite visit and should not be replaced by a telephone consultation unless an onsite visit is not feasible. Expected frequency of telephone contacts should be in line with the standard visit schedule, and therefore performed every 4 months. Ad hoc additional telephone contacts may also be requested (e.g. prior to the interim analysis) and made to the participant themselves or to other contact as provided by the patient, e.g. next of kin, primary physician (or local equivalent).

Note that study intervention may be temporarily discontinued (i.e. interrupted), as described in [Section 6.6](#).

See the SoA ([Section 1.3](#)) for data to be collected at the time of intervention discontinuation and follow-up and for any further evaluations that need to be completed.

### 7.1.1      **Temporary Discontinuation**

#### **Resumption of study intervention after temporary interruption**

Upon temporary interruption of the study intervention due to hyperkalemia, eGFR decrease, (S)AE, outcome events (OE), intolerance or any other reason, intake should be resumed as soon as medically acceptable at the discretion of the investigator. There is no defined maximum time limit for temporary interruption. In all cases, the reason for study intervention interruption must be recorded in the eCRF and the participant's medical records.

If the study intervention is interrupted for more than 7 days, the re-start should be performed at the next lower dose and the investigator should schedule an up-titration visit after 4 weeks ( $\pm$  7 days) in order to monitor potassium levels and renal function (see [Table 6–1](#)). If a regular visit will be scheduled to take place 4 weeks  $\pm$  7 days after up-titration or re-start, the monitoring of potassium and renal function is assured and no up-titration visit has to be performed in addition. A restart and/or safety check visit is expected only if the investigator is aware of a temporary interruption that was initiated by the study participant.

## 7.2 Participant Discontinuation/Withdrawal from the Study

- A participant may withdraw from the study at any time at his/her own request, or may be withdrawn at any time at the discretion of the investigator for safety, behavioral, compliance, or administrative reasons. This is expected to be uncommon.
- At the time of discontinuing from the study, if possible, a premature discontinuation visit should be conducted, as shown in the SoA. See SoA (Section 1.3) for data to be collected at the time of study discontinuation and check for any further evaluations that need to be completed.
- The participant may be prematurely and permanently discontinued from the study intervention at that time.
- If the participant withdraws consent for disclosure of future information, the sponsor may retain and continue to use any data collected before such a withdrawal of consent.

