**Please note:**

- 1 month corresponds to 30 days
- Study visits should occur as close as possible to the specified time points in the protocol, but time windows are permitted as specified in the SoA
- At any scheduled or unscheduled visit, the dose of study intervention may be increased to the next possible higher dose, based on serum/plasma potassium level analyzed in the local laboratory and provided the participant was already on a stable dose for 4 weeks ±7 days.

Abbreviations: AE = adverse event; CKD-EPI = Chronic Kidney Disease Epidemiology Collaboration; D = Day; eGFR = estimated glomerular filtration rate; ECG = electrocardiogram; EOS = end-of-study; EQ-5D-5L = EuroQoL Group 5-dimension 5-level questionnaire; hs-TnT = high-sensitivity troponin-t; IxRS = interactive voice / web response system; med. = medication; KCCQ = Kansas City Cardiomyopathy Questionnaire; M = Month; NT-proBNP = n-terminal prohormone B-type natriuretic peptide; NYHA = New York Heart Association; O = on-site; PGIC = Patient Global Impression of Change; PGIS = PGI of Severity; PD = premature discontinuation; PT = post-treatment; SoA = schedule of activities; Tel. = telephone

- Randomization has to occur within 2 weeks of the Screening Visit. If the Screening Visit and Visit 1 (Day 1, Baseline) are performed on the same day, procedures listed for both visits are to be performed only once.
- Study visits to be conducted as a clinic visit or a telephone contact visit. These visits will alternate at 4-monthly intervals from Month 12 onwards with participant contact being made every 2 months.
- This visit should be performed for safety check after any up-titration (4 weeks ±7days) and after restart of study intervention following an interruption for >7 consecutive days. A full unscheduled safety visit should be performed within an adequate timeframe proposed by the investigator after down-titration for reasons other than hyperkalaemia, otherwise only potassium is to be rechecked (refer to [Table 6–1](#))

- d The PD Visit should take place as soon as possible but within 7 days after the last intake of study intervention. If the PD Visit cannot be performed within the timeframe specified, no PD Visit is required. All randomized participants will be followed until the study ends, even if they did not take study intervention or permanently discontinued study intervention.

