An **urgent HF visit** is defined as an urgent, unscheduled presentation with signs and/or symptoms of an acute HF decompensation requiring prompt medical attention and intensification of the existing HF treatment or initiation of a new HF treatment ([Hicks et al. 2018](#)). Further details and definitions will be provided in the Outcome/Endpoint Manual and Clinical Event Committee (CEC) Charter.

According to the addendum to International Council on Harmonisation (ICH) E9 ([ICH\\_E9 \(R1\) 2019](#)), the 5 attributes of the primary estimand are as follows:

- a) Population:  
As described by inclusion/exclusion criteria given in Section [5](#)
- b) Variable:  
Number of unfavorable events including CV death and total (first and recurrent) HHF
- c) Treatment condition:  
Finerenone vs. placebo
- d) Intercurrent events:  
There are 3 important intercurrent events to consider: treatment discontinuation, CV death and non-CV death. For treatment discontinuation, a treatment policy strategy will be applied, i.e. patients will be followed up for events after discontinuing treatment and events and follow-up time after discontinuation of treatment will be included in the analysis. CV death will be counted as both an outcome event as well as a censoring event, so that a combination of a composite and a while-alive strategy is used. Non-CV death is assumed to be a censoring event, since the treatment is not assumed to have an effect on these events and interest lies in the treatment effect on composite events while patients are alive
- e) Population-level summary:  
Ratio of exposure-weighted composite event rates between finerenone and placebo. Exposure-weighted refers to patients being weighted according to their follow-up time in determining the rate.

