This study will be event-driven, and all randomized participants will remain in the study until either (1) an instruction is received from the sponsor after the targeted number of primary efficacy events has occurred, or (2) the study is terminated early at the recommendation of the DMC. Therefore, all participants, including those who have stopped taking study intervention, should be asked to attend all the protocol-specified study visits in order to perform all assessments as stipulated in the main SoA (Figure 1-1); for participants who permanently discontinued study intervention, minimal assessments (e.g. central lab for eGFR) will need to be performed as outlined in the Premature Discontinuation SoA (Figure 1-2). If a participant is unable to attend a study visit, every effort should be made to contact the participant by telephone or other means (by checking medical and public records) to determine if any endpoints were reached at the time the study visits were scheduled for the remaining duration of the study. All attempts to retrieve information about the participant should be documented in the participant's records.

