As treatment effects, a hazard ratio for CV death of 0.8 and a rate ratio for heart failure events of 0.75 are assumed. With approximately 5500 randomized participants, it is expected to observe approximately 1310 first events and approximately 2375 total events leading to a power of 90% to show an effect at a two-sided alpha level of 5%. Under these assumptions it is expected to observe a 19% decrease in the rate of the primary endpoint for finerenone. An annual drug discontinuation rate of 5% is assumed, with finerenone participants having the same risk of events as placebo participants after discontinuation and no change in event rate for discontinuing placebo participants. Participants discontinuing study intervention are expected to remain under observation in the study. [Table 9-1](#) below shows the resulting

power under deviations from the assumed treatment effect as well as the power for a time-to-first composite event analysis. As it would be desirable for a single pivotal trial to obtain a higher level of evidence so that the power at an alpha level of 1% is also given.

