#### **Female Participants who Become Pregnant**

- The investigator will collect pregnancy information on any female participant who becomes pregnant while participating in this study. The initial information will be recorded on the appropriate form and submitted to the sponsor within 24 hours of learning of a participant's pregnancy.
- The participant will be followed to determine the outcome of the pregnancy. The investigator will collect follow-up information on the participant and the neonate, after obtaining the signed informed consent from both parents, unless local law or specific circumstances of the respective case allow otherwise, and the information will be forwarded to the sponsor. Generally, follow-up will not be required for longer than 6 to 8 weeks beyond the estimated delivery date. Any termination of pregnancy will be reported, regardless of fetal status (presence or absence of anomalies) or indication for the procedure.
  - While pregnancy itself is not considered to be an AE or SAE, any pregnancy complication or elective termination of a pregnancy will be reported as an AE or SAE.
  - A spontaneous abortion (occurring at <22 weeks gestational age) or still birth (occurring at >22 weeks gestational age) is always considered to be an SAE and will be reported as such.
- Any post-study pregnancy related SAE considered reasonably related to the study intervention by the investigator will be reported to the sponsor as described in Section 8.3.4. While the investigator is not obligated to actively seek this information in former study participants, he or she may learn of an SAE through spontaneous reporting.
- Any female participant who becomes pregnant while participating in the study will discontinue study intervention or be withdrawn from the study.

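### Protocol Section 7.2 lets the investigator end a participant's study follow-up, against the rule that all randomised participants are followed to study end; the direction and size of any bias are unknown

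*Protocol*

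**What the plan says.** **When follow-up stops.**
- Protocol 7.2: a participant "may be withdrawn at any time at the discretion of the investigator for safety, behavioral, compliance, or administrative reasons". The only qualifier is "This is expected to be uncommon".
- Protocol Appendix 4 (Section 10.4): a participant who becomes pregnant "will discontinue study intervention or be withdrawn from the study". Section 7.1 lists pregnancy only as a reason to stop study drug.
- SoA footnote d (Section 1.3): "All randomized participants will be followed until the study ends, even if they did not take study intervention or permanently discontinued study intervention".
- Protocol 4.1: "all randomized participants will remain in the study until either (1) an instruction is received from the sponsor" once the target events have occurred, or the study stops early on the data monitoring committee's recommendation. No third exit is given.
- Protocol 7.1: participants who permanently stop study drug "are expected to continue in the post-treatment follow-up period and to attend all protocol-specified study visits".

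**What the analysis assumes.**
- The primary estimand (Protocol 3, repeated in SAP 2) uses treatment policy for treatment discontinuation: "patients will be followed up for events after discontinuing treatment and events and follow-up time after discontinuation of treatment will be included in the analysis". Study withdrawal is not among its three intercurrent events.
- Protocol 9.2: "Participants discontinuing study intervention are expected to remain under observation in the study". No rate of study withdrawal is assumed.

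**What follows a study withdrawal.** The opening sentence of Section 1.3, SoA footnote p and SAP 3 point to continued visits. Against that, Section 4.1 assigns Figure 1-2 to participants who stopped study intervention. SAP 4.5.3 counts events only to the last informative visit when no later information exists. SAP 4.2 classes anyone who leaves the study early as a dropout.

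**The concern.** Stopping study drug already has its own path and visit schedule (Section 7.1, Figure 1-2). Section 7.2 adds a second path, out of the study altogether, on grounds that overlap with reasons to stop drug. Safety and compliance can depend on treatment and on prognosis; Section 2.3 names hyperkalaemia as an important identified risk. Loss of follow-up for such reasons may therefore be informative.

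If a site does end follow-up, the consequences differ by endpoint:
- Primary composite, total HF events and renal composite: events after the last informative contact are lost.
- NYHA class: a participant with no Month 12 value is mostly counted as not improved (SAP 6.2.2.1).
- KCCQ: later values are missing from a mixed model that uses all observed values.
- Mortality is better protected, because vital status is sought from public sources (Sections 4.4 and 7.3). Those searches do not recover HF events.

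At stake is whether the primary analysis estimates the treatment-policy effect that the plan defines.

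**Working it through.** **1. The rules side by side.** Footnote d and the first statement in Section 4.1 are unconditional. Section 7.2 adds an exit that neither mentions. The passages on what happens next do not settle it: Section 1.3 gives Figure 1-2 to those leaving the study, Section 4.1 gives it to those leaving study drug. SAP 3 expects early terminators to be asked to visits; SAP 4.5.3 provides for the case where nothing more is known. A site cannot tell from these whether to keep following a participant it has withdrawn.

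**2. The plan's own figures.** Inputs from Protocol 9.2: 5500 participants, 1:1; 24 months' accrual, 42 months in total; placebo rates per month of 0.0182 HF events, 0.005125 CV deaths and 0.0016 non-CV deaths; gamma frailty variance 5.0 shared by HF events and CV death; rate ratio 0.75 for HF events and hazard ratio 0.80 for CV death; 5% per year stop drug, take placebo risk and stay in follow-up. The simulation used an unstratified Andersen-Gill model with robust variance (3000 runs).

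| Quantity | Plan | Simulated |
|---|---|---|
| Power, two-sided 5% | 90% | 89.3% |
| Power, two-sided 1% | 74% | 73.8% |
| Total events | 2375 | 2378 |
| First events | 1310 | 1310 |
| CV deaths | 535 | 534 |
| Rate ratio | 0.81 | 0.810 |

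The plan's figures are reproduced with nobody leaving except by death or study end. The implied standard error of the log rate ratio is |ln 0.810| / (1.960 + 1.243) = 0.2107 / 3.203 = 0.066.

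**3. Loss not tied to prognosis.** Assume a share of those who stop drug, in both arms, also leave the study (1000 runs each).

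| Share leaving | Participants | Events | Mean rate ratio |
|---|---|---|---|
| 10% | 61 | 2360 | 0.810 |
| 25% | 152 | 2343 | 0.809 |
| 50% | 304 | 2301 | 0.807 |
| 100% | 608 | 2231 | 0.799 |

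Monte Carlo error is about 0.81 × 0.066 / √1000 = 0.002, so only the last row clearly moves. The downward drift is expected: leaving removes finerenone participants' off-drug time, which the model places at placebo risk.

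**4. Informative loss, by assumption.** Let a fraction q of one arm leave halfway through follow-up, with m times the average event rate, and nobody leave in the other arm. That arm loses a share q·m·0.5 of its events and q·0.5 of its person-time, so its rate is multiplied by

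(1 − 0.5·q·m) / (1 − 0.5·q).

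- q = 1%, m = 2: 0.990 / 0.995 = 0.9950. Finerenone arm only: 0.81 × 0.9950 = 0.806. Shift in log rate ratio 0.0050, or 0.0050 / 0.066 = 0.08 standard errors.
- q = 3%, m = 3: 0.955 / 0.985 = 0.9695. Finerenone arm only: 0.81 × 0.9695 = 0.785. Shift 0.0309, or 0.0309 / 0.066 = 0.47 standard errors.
- The same losses in the placebo arm only: 0.81 / 0.9950 = 0.814 and 0.81 / 0.9695 = 0.835.

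The simulation shows the same symmetry. Withdrawing 10% of those with a first HF event gives 0.786 if only in the finerenone arm (47 participants), 0.844 if only in the placebo arm (54), and 0.815 if in both (102).

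**The case against.** The strongest reply is that this is a general rule with a rare exception, and that continued follow-up is already provided for. Section 1.3, footnote p and SAP 3 do point that way. Section 7.1 is partly soft: participants are expected and encouraged to attend. Footnote d speaks mainly to drug status and, read literally, would rule out even a participant's own withdrawal. Section 7.2 expects few cases, reasons are recorded, and SAP 4.2 compares dropouts by arm, timing and reason. The trial is event-driven, so lost events mainly lengthen it. The pregnancy route is small in a population aged 40 and over. All of this limits the point. It does not remove it, because Section 4.1 and SAP 4.5.3 pull the other way and nothing listed recovers HF events after follow-up has ended.

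A reader might infer more: that such withdrawals will be commoner on finerenone and make the rate ratio look too favourable. The documents do not support that. They give no withdrawal rate. Treatment is blinded with sham titration, and the potassium and eGFR rules lead to changes in study drug, not to study exit. Worsening HF on placebo could prompt withdrawals that bias the result the other way.

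A reader might also infer that withdrawn participants are censored in every analysis. NYHA and KCCQ are not handled by censoring; for NYHA, excess withdrawal on finerenone would count against finerenone.

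**Conclusion.** The conflict is real and should be resolved. Section 7.2 and Appendix 4 allow an exit that footnote d and Section 4.1 do not, the estimand does not address it, and the sample size assumes that those who stop drug stay under observation. What happens to follow-up afterwards is unclear.

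The effect on the primary result is unknown in direction and size. Loss unrelated to prognosis is close to harmless (0.810 to about 0.807 with half of drug discontinuers leaving). One-arm informative loss of 1-3% at 2-3 times the average rate gives 0.806 to 0.785 if on finerenone, and 0.814 to 0.835 if on placebo, at most about half a standard error either way. The fractions, risk multiples and halfway timing are assumptions.

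One limit: SAP 1 refers to a protocol amendment dated 26 October 2022, later than the Amendment 2 text of 16 May 2022 reviewed here. Whether it changed Section 7.2 cannot be checked.

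**What to change.** - In Section 7.2, state that only the participant's own withdrawal of consent, or loss to follow-up, ends study follow-up.
- State there that safety, behavioural, compliance or administrative reasons at the investigator's discretion lead to continued follow-up under Figure 1-2 or, where visits are not possible, by the telephone or informant contact that Section 7.1 already describes.
- Reconcile the opening of Section 1.3, the Figure 1-2 wording in Section 4.1 and the study-withdrawal alternative in Appendix 4 with that rule.

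No rule on stopping study drug changes, and the participant's right to withdraw is untouched. The cost is protocol wording and a reminder to sites. The downside is that sites stay in contact with a few participants they might otherwise have released.
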